3.4. STUDY POPULATION

The study will be performed on 108 narcoleptic children to assess the effects of pitolisant compared with placebo in the relief of Excessive Daytime Sleepiness (EDS): children from 6 to less than 12 years of age and adolescents from 12 to less than 18 years of age more or less equally balance between age groups (at least 40%). Each age groups should be also more or less equally balance between genders (at least 40%), all of them suffering from narcolepsy with or without cataplexy.

Patients are allowed to continue their anticataplectic drugs, if they are at stable dosage for at least 4 weeks before the inclusion (V2), and this dosage should be maintained stable throughout the study (from V2 to V8).

The previous use of drug with a psychotropic effect, including psychostimulants for the treatment of EDS should be discontinued at V0 (D-28).

At V1 (D-14), all prohibited treatments should be stopped for at least 14 days.

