3.4.1. Inclusion criteria

- 1) Male and female children from 6 to less than 18 years of age (at V8) suffering from narcolepsy with or without cataplexy meeting the International Classification of Sleep Disorders (ICSD-3) criteria (Narcolepsy type 1 and 2). Diagnosis confirmed with polysomnography and Multiple Sleep Latency Test for patients without cataplexy (if these examinations were not performed within the last 12 months)
- 2) PDSS score \geq 15 during baseline period (V1+V2) / 2.

- 3) Patients should be free of non-authorized medication, in particular psychostimulant treatments as from the screening visit (V0) onwards.
- 4) Parents and patients old enough to understand who have expressed a willingness to participate in the study, who have signed and dated the informed consent form prior to beginning protocol required procedures.
- 5) In the opinion of the investigator, the patient must have adequate support to comply with the entire study requirements as described in the protocol (e.g., transportation to and from trial site, self rating scales and diaries completion, drug compliance, scheduled visits, tests).
- 6) Female pubescent patients shall use a birth control method, judged efficient by the investigator, throughout the study and during the month following treatment discontinuation.
- 7) Patients should benefit from appropriate healthy insurance system (only applicable where mandatory e.g. in France).

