## 4.1.3 IMP groups comparison

# 4.1.3.1 Main Inferential model

Unless otherwise specified, all the endpoints referred in detail in the following section will be analyzed according the same statistical model allowing a comparison of results between the studied endpoints. The significance of the difference between the IMP compared with placebo will be assessed through a general model of analysis of Covariance (ANCOVA) in which the studied endpoint at final time (noted Yf) constitutes the dependent variable of the model. Independent variables are (1) the baseline value of the studied endpoint (noted Yb) analyzed as a fixed covariate, (2) the treatment effect (Noted Trt) coded 0 (placebo) or 1 (IMP) (cell mean contrast formulation), and (3) the center considered as a random factor of the intercept constituted by a fixed part  $k_0$  and a random component N(0, $\sigma_c$ ). This model is summarized by the following expression:

 $Y_{if} = (k_0 + \zeta) + k_b Y_b + k_t Trt + \epsilon_i \quad \epsilon_i = N(0, \sigma) \text{ and } \zeta = N(0, \sigma_c) \text{ [general Model -1]}$ 

Note 1-This model does not assume a treatment-baseline interaction term (as required in CPMP, 2003). Our decision of using center as a random factor is justified by the useless estimate of each center, in focusing on the measurement of the standard deviation of the intercept. The treatment will be considered as fixed factor without center random component.

Note 2- This model is a Linear Mixed Model (LMM) as it combines random and fixed factors, assumes linearity of baseline and hypothesizes the studied endpoint distributed according to a normal (Gaussian) distribution. This model constitutes the main model used in this trial for all the studied endpoints unless otherwise specified.

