## Maintenance of Wakefulness Test 30-minute version

For this assessment the four test have been considered. Therefore, arithmetic means and sum on these 4 tests are computed.

**Mean value for each latency parameter**, in minutes, for a visit, will be estimated as the arithmetic mean of the 4 tests.

**Before this mean computation each latency parameter** (sleep onset, Stade I, Stade II, stade III and SP) must be recalculed to take into account the "Awake" status and the test duration:

- For a test, if "Awake"= "yes" then the sleep onset latency has to be considered at 30min (even if another value is entered).

- If a reported value is greater than 30min this value will be censured at 30min.

Number of Sleep onset in SP for a visit, will be computed as the sum of Yes (=1) of the 4 tests.

A survival response will be computed according to the "sleep onset latency" recalculed:

- Non-response (0=patient remained awake until 30 minutes) = Mean sleep onset latency ≥ 30min.
- Response (1=patient falling asleep before 30 minutes) = Mean sleep onset latency < 30min.

- Patient sleep diary
- Rate of cataplexy (WRC), Number of diurnal involuntary sleep attacks and episodes of severe daytime sleepiness (NSAE) and Number of hallucinations and sleep paralysis episodes (NHS) are weekly ratio computed as :

[Number of episodes of the concerned parameter in the period / Number of days in the period] \* 7

Whith Number of days in the period= Date of the last visit of the period - Date of the first visit of the period + 1

Results are rounded to to the nearest integer number.

- Night duration (NightD), in hours, is calculated as:

Wake-time (morning) - Hour of bedtime (evening)

The mean of night duration per day during the studied period is computed as:

Sum of night duration in the period / Number of days in the period

Whith Number of days in the period= Date of the last visit of the period - Date of the first visit of the period + 1

The result is rounded to one decimal place.

In case of several hours at the same date the following rule will be applied:

- For wake-time the last hour will be kept
- For bedtime the first hour will be kept

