## Analysis:

A negative Binomial Regression will be used according to the general model (section 2.2) for WRC estimated during the period V6-V7 (Justification Plazzi 2021) only in the type I Narcolepy patients (for other patients we don't have the baseline value). The WRC at baseline will be used as a fixed covariate and center as random (In case of non convergence of the model, this one can be updated).

The same way as the primary analysis (Including sensitivity analyses) will be performed: MAR and MNAR imputation and observed cases.

In addition,

- Descriptive statistics by treatment group during the following intervals: Baseline (D-28 to D0),
   Final DB last 6 weeks DB4=D21-D63 (i.e. V4-V7), Final DB last 2 weeks: DB2=D49-D63 (i.e. V6-V7) will be provided
- A supportive analysis will be to compare the proportion of patients such that WRC <1 between treatment groups (simple logistic regression providing OR with 95%CI)

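### The supportive WRC <1 comparison omits baseline cataplexy rate, and integer rounding turns its cut-off into a raw rate below 0.5 per week

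*SAP*

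**What the plan says.** **Supportive analysis.** SAP 4.5.3.2.3 (Weekly rate of Cataplexy, Analysis) plans to "compare the proportion of patients such that WRC <1 between treatment groups (simple logistic regression providing OR with 95%CI". It names no covariate and no condition on baseline, and it does not restate the population.

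**Main WRC analysis, same section.** This is a negative binomial regression: "The WRC at baseline will be used as a fixed covariate and center as random". It is run "only in the type I Narcolepy patients (for other patients we don't have the baseline value".

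**Default model.** SAP 4.1.3.1: "Unless otherwise specified, all the endpoints referred in detail in the following section will be analyzed according the same statistical model". That default is baseline-adjusted. The supportive bullet specifies something else.

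**Eligibility.** Protocol 3.4.1 admits children "suffering from narcolepsy with or without cataplexy meeting the International Classification of Sleep Disorders (ICSD-3) criteria (Narcolepsy type 1 and 2". Its only symptom-score threshold is a mean PDSS of at least "15 during baseline period (V1+V2) / 2", which measures sleepiness. Neither 3.4.1 nor 3.4.2 contains an attack count. Protocol 3.4 adds: "Patients are allowed to continue their anticataplectic drugs, if they are at stable dosage for at least 4 weeks before the inclusion (V2".

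**Derivation.** SAP 4.1.5.5 (Patient sleep diary) computes WRC as episodes divided by days, times 7, with days counted as last visit minus first visit plus 1. Then: "Results are rounded to to the nearest integer number".

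**The concern.** A child whose cataplexy is already rare at entry, naturally or on a stable anticataplectic drug, meets the criteria. If that child is still below the cut-off at the end, the child counts as a success in whichever arm he or she was allocated to. The proportion below 1 then reflects prior control as well as treatment. Baseline WRC is already collected and would absorb much of that variation, but this model leaves it out.

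The second issue is the cut-off. A reader will take WRC <1 to mean fewer than one attack a week. On the rounded variable it means something stricter, and how strict depends on which interval is counted.

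At stake is the precision and the meaning of a responder odds ratio that is easy to quote. No confirmatory claim depends on it.

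**Working it through.** The plan states no power, rate or effect for this comparison, so there is no figure to reproduce.

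**1. Numbers with cataplexy.** The planned size is 36+72 (SAP 4.2). The Protocol Introduction puts cataplexy at about 80%: 0.8 × 36 = 28.8 and 0.8 × 72 = 57.6, so about 29+58. SAP section 3 says one-third, which gives 12+24. Both are carried below.

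**2. Dilution, closed form.** Assume a share q is below the cut-off at baseline and stays there in both arms, and that success among the others is p. Then P = q + (1−q)p in each arm, and the risk difference shrinks by the factor (1−q). Neither q nor p is in the documents. The table assumes p = 0.20 on placebo and 0.50 on pitolisant.

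Power (two-sided 0.05) = Φ{[Δ − 1.96·√(P̄(1−P̄)(1/n₀+1/n₁))] / √(P₀(1−P₀)/n₀ + P₁(1−P₁)/n₁)}.

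Example, q = 0.3 and 29+58: P₀ = 0.3 + 0.7 × 0.2 = 0.44; P₁ = 0.3 + 0.7 × 0.5 = 0.65; OR = (0.65/0.35)/(0.44/0.56) = 2.36; P̄ = 0.58. Power = Φ[(0.210 − 0.220)/0.111] = 0.46.

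| q | Risk difference | OR | Power, 29+58 | Power, 12+24 |
|---|---|---|---|---|
| 0 | 0.30 | 4.00 | 0.80 | 0.40 |
| 0.1 | 0.27 | 3.14 | 0.67 | 0.32 |
| 0.3 | 0.21 | 2.36 | 0.46 | 0.22 |
| 0.5 | 0.15 | 2.00 | 0.31 | 0.16 |

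With p = 0.30 vs 0.50, the OR goes from 2.33 at q = 0 to 1.78 at q = 0.3. Power goes from 0.42 to 0.24 (29+58) and from 0.20 to 0.13 (12+24).

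**3. Chance imbalance.** The SD of the between-arm difference in low-baseline share is √[q(1−q)(1/n₀+1/n₁)]. At q = 0.3 it is √(0.21 × 0.0517) = 0.104 for 29+58, and √(0.21 × 0.125) = 0.162 for 12+24.

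**4. Effect of adding baseline WRC.** A simulation used 29+58 patients, Poisson-gamma counts over 15 days and rounded WRC. It did not force low-baseline children to stay low. The spread of rates is assumed, and 12+24 was not simulated.

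| Median baseline attacks/week | Share <1 at baseline | Power unadjusted | Power adjusted | Power, baseline ≥1 only |
|---|---|---|---|---|
| 1 | 0.45 | 0.47 | 0.56 | 0.33 |
| 2 | 0.28 | 0.47 | 0.61 | 0.38 |
| 4 | 0.15 | 0.40 | 0.50 | 0.28 |

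The median OR rose from 2.45-2.59 to 3.31-3.83 with adjustment. With no treatment difference, the unadjusted test rejected in 0.04-0.06 of trials. Of the low-baseline children, 55-85% were still below the cut-off at the end.

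**5. Rounding.** A rounded value below 1 must be 0, so the raw rate must be below 0.5.

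- V6-V7 at nominal days: 56 − 49 + 1 = 8 days. One attack is 7/8 = 0.875, which rounds to 1 and fails. Only zero attacks succeed. With the ±2-day windows the count runs from 4 to 12 days, and one attack gives 7/4 = 1.75 to 7/12 = 0.58, which still rounds to at least 1.
- D49-D63, which SAP 4.5.3.2.3 also labels V6-V7: 63 − 49 + 1 = 15 days. One attack is 7/15 = 0.47, which rounds to 0 and succeeds. Two attacks are 14/15 = 0.93, which rounds to 1 and fails, although 0.93 is below one a week.

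The two intervals differ because D63 is the nominal day of V8, after the placebo wash-out week.

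**The case against.** The strongest reply is that little depends on this. The analysis is labelled supportive, it is not one of the five tests in SAP 4.1.3.2, and the tested WRC model does adjust for baseline. The proportion below one attack a week at the end of treatment is a legitimate marginal quantity; the SAP does not claim that it measures movement across the cut-off. Chance imbalance is part of what the confidence interval covers, and baseline WRC is tabulated by arm. All of this stands, and it sets the severity.

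A reader might infer four stronger things that the documents do not support:

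- That many already controlled children enter. The criteria allow it, but no baseline distribution is given.
- That every such child is a success in both arms. That requires still being below the cut-off at the end.
- That the comparison is biased or inflates type 1 error. The simulated size was close to nominal.
- That a single attack is always scored a failure. That is true of the V6-V7 count but not of D49-D63.

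The size of the dilution also depends on what happens to low-baseline children. Take 30% vs 55% success among the others (OR 2.85) and a low-baseline share of 20%, 40% or 60%. If 90% of low-baseline children stay low in both arms, the pooled OR is 2.25, 1.90 or 1.63. If 70% on placebo and 85% on pitolisant stay low, it is 2.55, 2.38 or 2.30.

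Finally, part of the larger adjusted OR is only its conditional meaning. The power gain is the firmer argument.

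**Conclusion.** The point holds as a minor improvement. Leaving out baseline WRC costs power and leaves the estimate exposed to imbalance in prior control. At 30% low baseline, the SD of that imbalance is about 10 percentage points for 29+58 patients and 16 for 12+24. The simulated gain from adjustment is roughly 0.09 to 0.13 in power for 29+58. These sizes are illustrative: they rest on assumed baseline rates and success proportions, and on which of the two stated cataplexy shares applies.

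The rounding result needs no distributional assumption, only that the derived, rounded WRC is the variable that is dichotomised. The SAP does not say otherwise.

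The natural reading is that the supportive bullet inherits the type 1 restriction of its section. If it did not, children without cataplexy would also count as successes and the dilution would be larger.

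**What to change.** In SAP 4.5.3.2.3:

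- Replace the simple logistic regression by one with treatment and baseline WRC, for example log(WRC + 0.5) so that zero baselines are usable, and state that it is run in type 1 patients.
- Apply the <1 cut-off to the unrounded rate, and name one interval for the final rate and one for the baseline rate. The interval matters even without rounding: one attack gives 7/8 = 0.875 in an 8-day count but 7/7 = 1.00 if the visits fall a day closer, so a short count lets visit timing decide the outcome.
- Optionally show the proportions by arm among children with baseline WRC ≥1, as a descriptive sensitivity analysis only. Restriction looks helpful in the closed-form case (power 0.63 against 0.46 at q = 0.3, 29+58), but only because that case assumes that low-baseline children never change. In the simulation, restriction alone lowered power to 0.28-0.38.

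The cost is two or three sentences and no new data. The odds ratio becomes conditional on baseline, so the observed proportions by arm should be shown beside it.

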# Missing data handling:

Multiple Imputation (MI) procedure will be used to impute the missing evaluations (Cf.section 4.1.4.1).

# Statistical elements:

For this comparison the following elements will be provided in a summary table:

- Estimate (standard error) of the difference between adjusted treatment group means.
- Two-sided 95% CI of the estimate.
- p-value (to be compared to 0.05).

## 4.5.3.2.4 Maintenance of Wakefulness Test 30-minute version

The Maintenance of Wakefulness Test (MWT) is used in this study to assess an individual's ability to maintain awake while resisting the pressure to fall asleep. Patients will be administrated four 30-minute MWT sessions at 2-hour intervals at inclusion visit (V2) and at endpoint visit (V7 or the last on-study visit). Each session is terminated either at the first unequivocal onset of sleep defined as above or, if sleep onset is not achieved, after maximum in-bed duration of 30 minutes.

## Analysis:

MWT was right censored after 30 minutes, resulting into a truncated asymmetric distribution (Plazzi 2021).

A Cox proportional regression will be conducted in considering time to sleep onset (mean of the 4 tests at final visit) and survival response defined as non-response (0=patient remained awake until 30 minutes) and response (1=patient falling asleep before 30 minutes). Patients early terminating for treatment-related or -unrelated reason will be considered as responders or right-censored at the time of interruption, respectively. Center will be considered as a cluster variable in the Cox model to allow calculation of robust variance for the model assuming clusters with correlated observations [Andersen 1982, Therneau 2000].

This analysis will be done only in patients with at least a baseline value or a final value (V7 or the last on-study visit).

The same way as the primary analysis (Including sensitivity analyses) will be performed: MAR and MNAR imputation, center as fixed effect (in MAR imputation) and observed cases.

Descriptive statistics (mean values for each latency parameter and number of Sleep onset in SP) at baseline and V7 by treatment group will be provided.

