#### 4.1.4 Missing data

#### 4.1.4.1 General considerations

(ICH E3; 9.7.1, 11.4.2.2. ICH E9; 5.3. EMA Guideline on Missing Data in Confirmatory Clinical Trials) Missing data will be imputed for five main endpoints of this study (UNS, PDSS, UNS-CTP, WRC and MWT). For the other endpoints no missing value will be imputed.

A Multiple Imputation (MI) procedure will be used to impute the missing evaluations, as a prior step, assuming that those patients would be in their randomized arm. The partially complete datasets will be generated with a model including the following covariates age, gender and the main model components (section 2.2).

A total of 100 imputed partially complete datasets will be generated.

MI inference involves 3 consecutives phases:

- 1/ Imputation step:

The missing pattern is supposed to be monotone, so the regression method will be used to impute missing data.

The partially complete datasets will be generated with a model including age, gender factors and taking into account the baseline score of the primary endpoint, based on patient which every postbaseline measurement available. It is of note that this imputation step might be preceded by one MI approach based on MCMC method, in case of arbitrary missing pattern. A total of 100 imputed partially-complete datasets will be generated.

The mean MD imputation will based on Missing at Random (MAR) corresponding to the hypothesis that missingness is assumed independent of the outcome, or to estimate a "de jure" (per protocol) estimand, censoring after any protocol deviation. This hypothesis was considered as the most likely in this particular context.

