Despite the likelihood of this option, a secondary MD imputation will be conducted according to the Missing at Random hypothesis (MNAR), for which several options to construct the joint distribution of the observed and unobserved data have been proposed, each reflecting a different MNAR mechanism (Carpenter et al., 2013). This appropriate choice was discussed in the general context of narcolepsy. We assumed that after dropping out, participants from the active arm have the same outcomes as the reference group individuals, hypothesizing that the treatment effect is lost after the individual leaves the study. This option is called Jump to reference (J2R), after dropout, the participant's conditional outcomes are associated to those of the control arm. The joint distribution is a Multivariate Normal model with mean parameters from the randomised arm until date of interruption (Di) and from the reference group afterward. The covariance matrix corresponds to the parameters from the randomised arm until Di and to the reference group for the conditional components of the post-dropout variables, given the pre-dropout measurements.

Concerning the J2R, the jump-to-placebo approach will be set up for these patients' imputations, by using the %mistep macro from James Roger (https://www.lshtm.ac.uk/research/centres-projects-groups/missing-data#dia-missing-data, zip file MISTEP20180327).

Usualy, a sequence of %mistep is run, the subsequent models include the residuals of the previous model. In this study only one model will be used (for the endpoint value imputation).

In case of imputed data outside the range, the minimun or the maximun bound will be used.

This macro will be used because no SAS procedure are currently available to perform the jump to reference approach.

- 2/ Analysis step:

The same analysis as described above will be applied to each of the 100 imputed datasets.

- 3/Combination step:

Statistical inferences will be generated by combining results from 100 analyses using Rubin's formulae (Rubin, 1987).

The multiple imputation estimator of the difference between active treatment and placebo is the average of the individual 100 estimators. The variance of the estimator is the combination of the between and within-imputation variability (Kenward & Carpenter, 2007).

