## 4.5.3.1.1 Primary analysis

Analysis:

In order to meet the primary objective of the study, the superiority of Pitolisant (BF2.649) as compared to placebo on efficacy after a 7-week treatment period will be assessed, from the UNS total score expressed in terms of change from baseline to Final value. After a Multiple Imputation, the main inferential model with the center as random effect described in section 4.1.3.1 will be used. The assumptions underlying the model will be checked.

The difference between treatment groups will be calculated as BF2.649 minus placebo. Thus, considering the main analysis, a negative treatment difference will be in favour of BF2.649.

The ICH-E9(R1) addendum on Estimands and Sensitivity Analysis in Clinical Trials (ICH, 2020) provides a framework for defining an estimand which is characterized by five attributes: population, endpoint, intercurrent events and population-level summary. The primary estimand for the primary endpoint of the study is defined with mixed strategies for intercurrent events and described in this table (based on the estimand terminology).

The following table summarizes the main endpoint according to the Estimand Notation (ICH-E9R1):

Attribute 	Primary definition		Rationale (as needed)
Population	Intended to include narcoleptic children from 6 to less than 18 years of age with/without cataplexy.		
Endpoint	Ullanlinna Narcolepsy Scale (UNS) at V6, V7		
		•	
Intercurrent events	Event	Strategy	Rationale (as needed)
	Receipt of assigned study treatment	Treatment policy	Strategy applied to align the estimand with the application of the ITT principle.
	Prohibited concomitant medication during the study treatment period	While on treatment	Strategy applied to assess the treatment effect up to the last observation at or prior to the time of the prohibited concomitant medication, which marks the end of adherence to treatment.
	Premature discontinuation from the study at any time	Hypothetical strategy	Strategy applied to estimate what the treatment effect would have been if patients adhered to the treatment by assuming that missing data arise from a missing at random (MAR) mechanism.
Population	Difference in LS means from ANCOVA model		
summary	between treatment groups.		

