## Missing data handling:

Multiple Imputation (MI) procedure will be used to impute the missing evaluations (Cf.section 4.1.4.1).

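### The MWT rule that makes early terminators events or censored at interruption has no value on the 0–30 minute Cox axis and conflicts with the planned imputation

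*SAP*

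**What the plan says.** SAP 4.5.3.2.4 analyses MWT with a Cox model. The time variable is the mean sleep-onset latency over four 30-minute sessions at the final visit. SAP 4.1.5.5 caps latency at 30 minutes and derives the event code from latency alone: a mean below 30 is the event and 30 is censored. A responder here is therefore a patient who fell asleep.

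The Analysis paragraph of 4.5.3.2.4 then gives a dropout rule: "Patients early terminating for treatment-related or -unrelated reason will be considered as responders or right-censored at the time of interruption, respectively".

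The same paragraph also plans "MAR and MNAR imputation, center as fixed effect (in MAR imputation) and observed cases". It restricts the analysis as follows: "This analysis will be done only in patients with at least a baseline value or a final value (V7 or the last on-study visit"). Under Missing data handling it adds: "Multiple Imputation (MI) procedure will be used to impute the missing evaluations (Cf.section 4.1.4.1"). SAP 4.1.4.1 agrees: "Missing data will be imputed for five main endpoints of this study (UNS, PDSS, UNS-CTP, WRC and MWT"). That section also keeps imputed values on the scale: "In case of imputed data outside the range, the minimun or the maximun bound will be used".

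Under Statistical elements, 4.5.3.2.4 asks for a difference between adjusted group means.

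**The concern.** Two things do not fit together.

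- **No value on the axis.** The Cox clock runs from 0 to 30 minutes within a test session. Leaving the trial happens on a study day. The rule gives a status (event or censored) but no time in minutes, so it cannot be applied as written.
- **Two rules for the same patients.** A patient who leaves before V7 normally has no final MWT. The rule above makes that patient an event or a censored observation; the imputation text gives the same patient an imputed latency. No text withdraws the first rule or calls it a sensitivity analysis.

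MWT is a confirmatory secondary endpoint. If this is settled only after unblinding, the choice of rule and of minute value could depend on the result.

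**Working it through.** **1. The passages side by side**

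| Place | Patient without a final MWT |
|---|---|
| SAP 4.5.3.2.4, Analysis, early-termination sentence | Event or censored by reason; no minute value |
| SAP 4.5.3.2.4, Analysis, last part, and Missing data handling | Imputed under MAR and MNAR; observed cases as well |
| SAP 4.1.4.1 | MWT among the five imputed endpoints; result in minutes, held to the bounds |
| SAP 4.1.5.5 | Status from latency only; no dropout rule |

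**2. Who is affected.** The schedules (protocol synopsis and SAP Table 1) place MWT at V2 and V7 only. Protocol 5.2.10 lists no MWT for premature withdrawal. The condition of a baseline or a final value keeps these patients in the analysis, so both rules reach them.

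**3. Size.** The documents give no MWT event count, hazard ratio, power or dropout rate, so there is no figure to reproduce. What follows is an illustration on assumed inputs.

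- Group sizes: 36 placebo + 72 drug (SAP 4.2).
- Pooled dropout, assumed: 2/27 = 7.4%, from protocol 7.7.2, where 25 of 27 randomised patients had V6 and V7 values (exact 95% CI 0.9–24%).
- Arm rates, from (36·p_placebo + 72·p_drug)/108 = 7.4%. For drug 2:1, 180p/108 = 7.4% gives p = 4.4% placebo and 8.9% drug. For drug 3:1, 252p/108 = 7.4% gives 3.2% and 9.5%. With placebo higher, the rates are 11.1%/5.6% (2:1) and 13.3%/4.4% (3:1).
- Also assumed: log-normal latency with median 8 minutes (log-scale SD 0.8 between and 0.5 within patients), half of dropouts treatment-related, interruption uniform on days 1–56, no true effect.
- Model: treatment-only Cox with model-based SE; 10,000 trials per pattern.

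False positives for the drug (nominal 2.5%), by how interruption is entered:

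| Dropout placebo / drug | Weeks | 0 min | Days as minutes |
|---|---|---|---|
| 7.4 / 7.4% | 2.8% | 2.8% | 2.9% |
| 4.4 / 8.9% | 2.6% | 2.3% | 6.8% |
| 3.2 / 9.5% | 2.4% | 1.9% | 8.8% |

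With placebo dropout three times higher, weeks gave 4.1–4.6% in repeat runs and 0 minutes about 5.4%, both for the drug. Days gave 7.2% (2:1) and 12.8% (3:1) against the drug. Days mislead because a mean interruption of (1+56)/2 = 28.5, read as minutes, outlasts most patients when the median is 8. Imputation as the single rule gave 2.5–3.5% for the drug in every null pattern run.

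**4. Power.** With an assumed true hazard ratio of 0.60 (67% power without dropout):

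| Dropout | Weeks | 0 min | Imputation | Days as minutes |
|---|---|---|---|---|
| Equal | 63% | 62% | 65% | 49% |
| Drug 3:1 | 59% | 57% | 65% | 73% |
| Placebo 3:1 | 67% | 69% | 64% | 22% |

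**5. Dependence on the reason for leaving.** A separate simulation used exponential latency, hazard ratio 0.6, and 6 drug and 2 placebo dropouts. When all were censored, every rule gave a hazard ratio near 0.60 and power 0.60–0.61. When all were treatment-related, imputation gave power 0.60 and an event near 0 minutes gave 0.51.

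**The case against.** **Imputation already leads.** SAP 4.1.4.1 makes imputation a step before the analysis, 4.5.3.1.1 fits the main model after it, and the MWT section follows the primary analysis. Premature discontinuation is handled there "by assuming that missing data arise from a missing at random (MAR) mechanism". A reader might infer that the plan gives no hint of precedence and cannot be programmed at all. The documents do not support that: they point to impute, derive the event code, then fit. What stands is that the contrary sentence is still in the Analysis paragraph, neither withdrawn nor labelled.

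**A stopped session may be meant.** The MWT section does speak of sessions being terminated, so this reading cannot be ruled out. It fits poorly: the sentence concerns patients with treatment-related reasons, the time variable is a mean of four sessions, and SAP 4.1.4.1 uses the word for leaving the study ("until date of interruption (Di) and from the reference group afterward").

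**The large error rates need a unit error.** A reader might infer serious type I error inflation. That arises only if trial days are entered as minutes, which no text suggests. The objection stands.

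**7.4% is not a dropout rate.** Protocol 7.7.2 reports an interim look at the then-primary endpoint and does not say that the other two patients had left or lacked MWT. This also stands; the figure is an assumption.

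**Counting treatment-related discontinuation as failure is legitimate.** So it is, but it needs a defined minute value and a stated role.

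**Conclusion.** The defect is real and textual: the sentence cannot be applied to a time variable in minutes, and it conflicts with the imputation planned for the same patients. It is a conflict to clear up before unblinding, not evidence that the MWT test is invalid.

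Its size is unknown. On the assumed inputs, false positives for the drug stay at about 2–4% as weeks (4.6% in one run) and about 2–5% as 0 minutes, highest when placebo has more dropout. Days entered as minutes would give about 6–9% for the drug when its dropout is two to three times higher, and 7–13% against it when placebo dropout is higher. The direction depends on dropout by arm and on the reasons for leaving, neither of which is given. The simulation omits the planned centre clustering and the baseline covariate.

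MWT is fifth and last in the fixed sequence (SAP 4.1.3.2), so UNS, PDSS, UNS-CTP and WRC are unaffected.

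**What to change.** Amend SAP 4.5.3.2.4 before unblinding:

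1. Remove the early-termination sentence from the main MWT analysis and state: *In the MAR and MNAR analyses a missing final MWT is imputed on the 0–30 minute scale, with baseline MWT (not the UNS baseline), age, sex and the main model components as covariates; under MNAR, treatment is handled by the jump-to-reference rule. Values outside the range are set to the nearer bound. The event code is then derived as in 4.1.5.5. Observed cases stay as planned.* Baseline MWT must be named because the imputation step in 4.1.4.1 refers to the baseline of the primary endpoint. If the sponsor keeps the event/censor rule, label it a sensitivity analysis and state the minute value given to a dropout.
2. Under Statistical elements, report the hazard ratio with its 95% CI and p-value, because a Cox model yields no difference in adjusted means. Mean latency stays as description.
3. Reconcile the final-visit definition (V7 or the last on-study visit; protocol 3.7.1.2.5 and SAP 4.5.3.2.4) with the schedules, which have no MWT at premature withdrawal. Use an off-schedule MWT only if one was performed.

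The cost is SAP wording. No new data are needed, and the imputed and observed-cases analyses are already planned.
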